Patients will be randomized to treatment with either bucindolol or placebo in a double blind design that will be stratified based upon etiology of heart failure, gender, ejection fraction, race and the hospital at which they are treated. Etiology of congestive heart failure will be divided into presence or absence of coronary artery disease (CAD). For the purpose of the study, coronary artery disease will be defined as either: (1) a history of previous myocardial infarction (MI), diagnosed by ECG (Qwaves) or enzymes, (2) evidence of significant obstruction, greater than 70% diameter luminal narrowing of at least one major epicardial artery with corresponding regional wall motion abnormality, (3) an unequivocally positive stress perfusion study demonstrating coronary artery disease, (4) an exercise stress test in a patient with an interpretable ECG (i.e. no BBB, LVH, or ST-T changes at baseline, and not on digitalis), who demonstrates provokable ischemia (i.e. 2 mm or more of flat or down sloping ST - depression at 80 msec after the J-point). In the case of positive ETT and normal angiography, the patient will be classified as non-CAD. While coronary angiography or stress perfusion is not mandated for entry, the investigator is expected to determine the etiology of ventricular dysfunction as part of the patient's routine care. Following randomization, patients will be started on a twice daily treatment regimen consisting of either bucindolol 3.0 mg, or placebo. Doses of drug will be titrated over a 5-9 week period as tolerated with the ultimate goal of reaching a dose of bucindolol of 200 mg PO daily (100 mg PO twice daily) for patients weighing greater than or equal to 75 kg at randomization, and 100 mg daily (50 mg PO twice daily) for patients weighing less than 75 kg at randomization.

D. Study size and duration

The recruitment will extend for 3 years and there will be a minimum follow-up of 1.5 years (*note: patient accrual was extended by 7 months*). The study will have a 85% power to detect a 25% mortality reduction. Based on these considerations, a target sample size of 2800 randomized patients with equal numbers assigned to each treatment group is needed (see Appendix A for sample size calculation).

E. Drug Rationale

Rationale for drug selection

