5. DESCRIPTION OF TREATMENT GROUPS

5.01 Outline of Study Design

The primary objective of this prospective, randomized, double-blind study is to evaluate the effect of β -adrenergic blockade on all cause mortality in patients with moderate to severe chronic heart failure in spite of conventional medical therapy. The basic study design is outlined in Figure 1.

[FIGURE 1]

```
Patient Eligible and Consenting? \rightarrow No \rightarrow EXCLUDE

\downarrow

Yes

\downarrow

RANDOMIZE

\downarrow

Bucindolol HCI

Placebo
```

Patients screened by study personnel and found to be eligible for participation in the study will be stratified according to (1) the hospital site and (2) the presence or absence of coronary artery disease. Patients will be treated and followed serially until death, refusal to continue study follow-up or termination of the study. Approximately 2,800 patients will enter the study during the three year enrollment period. The study will have a total duration of 4.5 years.

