6.02 Maintenance Treatment Phase

Beginning the day of Visit 10 (6-month visit), patients will enter a maintenance treatment period for the duration of the study. During this period, patients return to the study clinic for Visit 10 (6-

month visit), Visit 11 (12-month visit) and then subsequent follow-up visits every six-months thereafter. [NOTE: It can be anticipated that some patients will need to return to the study clinic more frequently (e.g., every 4-8 weeks) due to the severity of their illness.]

At Visit 10 (6 month visit) and all subsequent follow-up visits thereafter, the study drug should be prescribed at the highest tolerated dose without side effects. For example, if the highest tolerated dose administered to a patient during Part II of the start-up phase was 25 mg BID, then the dose prescribed at Visit 10 should be 25 mg BID; if the highest tolerated dose administered to a patient weighing > 75 Kg during Part II of the start-up phase was 100 mg BID, then the dose prescribed at Visit 10 should be 100 mg BID. *(NOTE: A dose as low as 3 mg BID will be allowed.)*

During the maintenance treatment phase, if intolerable side effects occur with B-395 (any dose), the dose of study drug may be reduced temporarily or permanently, if necessary (see Section 10, Discontinuation of Study Drug for Clinical Reasons). The patient may at some later time tolerate re-titration to a higher dose.

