7.02 Patient Kit Designs

7.02(a) B-395 Titration Kits

These are the only kits that CSPCRPCC will ship to each participating medical center prior to activating the study. All Titration Kit assignments will be made by the Palo Alto Cooperative Studies Program Coordinating Center (CSPCC). *(NOTE: Titration Kits may or may not be assigned in numerical order.)* Titration Kits contain B-395, either active or placebo. Each kit has six bottles of study drug. The study drug will be available in six clearly marked dosage forms: 3 mg, 6.25 mg, 12.5 mg, 25 mg, 50 mg, and 100 mg capsules.

Each Titration Kit contains a three month (98 days) supply of study drug and the bottles within each kit will contain varying quantities of drug:

	Drug	# Bts/Kit	Dosage Form	# Caps/bt
B-395	3 mg	1	3 mg capsules	196s
B-395	6.25 mg	1	6.25 mg capsules	182s
B-395	12.5 mg	1	12.5 mg capsules	168s
B-395	25 mg	1	25 mg capsules	210s
B-395	50 mg	1	50 mg capsules	189s
B-395	100 mg	1	100 mg capsules	126s

Each Titration Kit is identified with a specific kit number. Upon randomization, the Palo Alto CSPCC will assign each patient his own Titration Kit.

7.02(b) B-395 Maintenance Kits

Each B-395 Maintenance Kit will be identified with the same number as on the patient's Titration Kit. [NOTE: Drug assignment (active or placebo) also will be the same as in the patient's *Titration Kit.*] Each kit contains a 12-month supply of medication and each bottle has enough medication to treat the patient for three months (98 days). Subsequent Maintenance Kits will be prepared by CSPCRPCC and automatically shipped to each participating medical center.

POSSIBLE CONTENTS OF B-395 MAINTENANCE KITS

CODE NAME	STUDY DRUG	QUANTITY
B-395 3 mg	Bucindolol HCl or placebo OR	4 bottles (196)*
B-395 6.25 mg	Bucindolol HCl or placebo OR	4 bottles (196)
B-395 12.5 mg	Bucindolol HCl or placebo OR	4 bottles (196)
B-395 25 mg	Bucindolol HCl or placebo	4 bottles (196)
B-395 50 mg	Bucindolol HCl or placebo	4 bottles (196)

4 bottles (196)

(* number in parenthesis is the number of capsules in each bottle)

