9.01 (b) B-395 Transition Bottles

On the day of Visit 9 (3-month visit), the patient must be prescribed ONE of the six types of Transition Bottles available in Pharmacy. The type of bottle prescribed for this visit will likely depend on the highest dose tolerated by the patient during the titration period. Each Transition Bottle contains a 3-month supply (98 days) of study drug. *(NOTE: Transition Bottles are not patient-specific until assigned by the Albuquerque CSPCRPCC. Remember...study personnel must call the CSPCRPCC for all Transition Bottle assignments.)*

9.01 (c) B-395 Maintenance Kit Bottles

On the day of Visit 10 (six-month visit) and at each of the follow-up visits outlined below, the patient will be prescribed TWO bottles of study drug. The type of Maintenance Kit bottles automatically shipped by CSPCRPCC for each patient will be based on either (1) the type of Transition Bottle assigned to the patient at Visit 9 or (2) the last type of Transition Bottle assigned to the patient at Visit 9 or (2) the last type of Transition Bottle assigned to the patient at any other time during the transition period (i.e., other than at Visit 9). Each bottle in the patient's Maintenance Kit will be numbered consecutively. The bottles should be dispensed in numerical order to facilitate recordkeeping.

MAINTENANCE PHASE DISPENSING SCHEDULE

	Follow-Up Visit:	10 (6-	Number of B-395 Bottles To Dispense:
month)			2 bts (196)*
	11 (12-month)		2 bts (196)
	12 (18-month)		2 bts (196)
	13 (24-month)		2 bts (196)
	14 (30-month)		2 bts (196)
	15 (36-month)		2 bts (196)
	16 (42-month)		2 bts (196)
	17 (48-month)		2 bts (196)
	18 (54-month)		NO MEDICATION DISPENSED

(* the number in parenthesis is the number of capsules in each bottle)

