9.04 Prescriptions for Study Drug

The study drug can be ordered on either a standard prescription blank or a doctor's order sheet (in-patient only). Each time the study drug is prescribed, however, an order must be signed by the investigator or one of the other authorized physicians. Each prescription or doctor's order sheet must provide the following information:

- a. Patient's name, social security number (VA SITES ONLY) and current address
- b. Study identification: CSP #395
- c. Patient's B-395 Titration Kit number
- d. Drug code name and dose: B-395 3 mg, B-395 6.25 mg, B-395 12.5 mg, B-395 25 mg, B-395 50 mg, or B-395 100 mg capsules

e. Amount to be dispensed (refer to Dispensing Schedule, Section 9) f.Directions

- g. Signature of investigator or other authorized physician
- h. Date prescription is written

i. Refills (local policy permitting)

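### Minor: Appendix B was not updated for the 7-month accrual extension; 5.01 still gives 4.5 years, and the 9.01(c) table stops drug and visits at month 54 although planned follow-up can reach month 61

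*Protocol*

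**What the plan says.** **Main body.** Section II.D keeps three years of recruitment and a minimum follow-up of 1.5 years, and adds in a note that "patient accrual was extended by 7 months". Section XIII places the planned end 1.5 years after the last participant is randomized, and allows an earlier or later date. Section VII.D.2 has six-monthly visits after year 1 and names no last visit.

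**Appendix B, 5.01.** Enrollment is given as three years, and "The study will have a total duration of 4.5 years". The same section has patients treated and followed until death, refusal of further follow-up or the end of the study.

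**Appendix B, 6.02.** From the 6-month visit, "patients will enter a maintenance treatment period for the duration of the study". The prescribing rule is: "At Visit 10 (6 month visit) and all subsequent follow-up visits thereafter, the study drug should be prescribed at the highest tolerated dose".

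**Appendix B, 9.01(c).** The table lists two bottles at each visit from month 6 to month 48. At Visit 18 (month 54) the entry is "NO MEDICATION DISPENSED". That is the last row.

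**Appendix B, 9.04.** Every prescription must carry this item: "Amount to be dispensed (refer to Dispensing Schedule, Section 9".

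**The concern.** The main text lengthens the study, but the drug-handling appendix does not. A pharmacist with an early enrolee at month 54 holds two instructions. Section 6.02 says to keep prescribing. The table, to which 9.04 points for the amount to dispense, says to give nothing and shows no further visit.

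Two things are at stake. Patients who lose drug this way still contribute deaths to the intention-to-treat comparison, so any real effect would be diluted, though very slightly. There is also patient care: VII.D.3 and Appendix B 9.03 both warn that abrupt withdrawal of beta-blockade has been linked to cardiovascular events, so an out-of-date table row should not prompt an unplanned stop.

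**Working it through.** **Inputs**
- Accrual: 36 months, plus 7 months' extension (II.D).
- Minimum follow-up after the last randomization: 18 months (II.D, XIII).
- Supply: two bottles per visit (9.01(c)), 98 days each (Appendix B 7.02(b)).
- Target enrollment: 2800 (II.D).
- Assumed, because the documents give no accrual curve for the extended period: uniform accrual of 2800 patients over 43 months, and constant annual mortality between 10% and 15%. (Appendix A uses 15% for placebo before adjustment.)

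**Step 1. Reproduce the plan's figure.** Longest follow-up = accrual + minimum follow-up = 36 + 18 = 54 months = 4.5 years. This matches 5.01 and the month-54 row exactly, so that row marks the end of study under the old calendar.

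**Step 2. Apply the extension.** 36 + 7 + 18 = 61 months = 5.08 years. Six-monthly visits up to month 61 include month 54 as an ordinary visit and add one at month 60.

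**Step 3. Find the end of supply under the table.** The last dispensing is at month 48. 2 x 98 = 196 days; 196 / 30.44 = 6.44 months; 48 + 6.44 = month 54.44. The longest gap is 61 - 54.44 = 6.56 months.

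**Step 4. Count the patients concerned.** Follow-up passes month 54 for those randomized in the first 7 months: 7/43 = 16.3%, and 0.163 x 2800 gives about 456. Alive at month 54: 456 x 0.85^4.5 (0.481) = 219, or 456 x 0.90^4.5 (0.622) = 284.

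**Step 5. Compute the uncovered person-time.** With S(t) = (1 - m)^(t/12), and (61 - t)/43 as the share of patients with planned follow-up beyond month t (for t above 18):

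uncovered = 2800 x integral from 54.44 to 61 of S(t) (61 - t)/43 dt

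Without deaths the integral is 6.56^2 / 86 = 0.50 months per patient randomized. With deaths:

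| Annual mortality m | Uncovered patient-years | Total patient-years | Share |
|---|---|---|---|
| 15% | 54.3 | 6,995 | 0.78% |
| 10% | 71.0 | 7,676 | 0.93% |

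A slower start to accrual lowers this. If the rate rises linearly over the first 12 months and is then constant, the share is 0.17% to 0.21%. If it rises over all 43 months, the share is 0.09% to 0.11%.

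**Step 6. Set the sections side by side.**
- 5.01 (three years, 4.5 years) against II.D and XIII (43 months, up to 61 months): conflict.
- 9.01(c) (no drug at month 54, no later row) against 6.02 (drug at all visits while the study runs): conflict once the study runs past month 54.
- 5.01 against 6.02: no conflict. 6.02 states no length, and 5.01 also treats until the study ends.

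**The case against.** The best defence is that the treatment rule is already right elsewhere. Sections 5.01 and 6.02 both continue treatment to the end of the study, the main-body visit schedule is open-ended, and the pharmacy centre sends supplies unprompted: "Subsequent Maintenance Kits will be prepared by CSPCRPCC and automatically shipped to each participating medical center". Section 9.04 lists what a prescription must contain and points to Section 9 for the amount, not for whether a patient stays on drug. The preface also allows updates by supplemental memoranda, which are not shown, and XIII leaves close-out procedures to the Steering Committee. All of this stands. It makes the drug gap conditional on a site following the table over 6.02. It does not make the table or the duration in 5.01 correct.

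A reader might infer more than the documents support, in three ways.
- **That 5.01 contradicts 6.02.** It does not, as Step 6 shows; 5.01 is at odds with II.D and XIII.
- **That the plan decided to stop treatment at month 54, or that patients did go without drug.** The row coincides exactly with the old end of study, and nothing shows what sites did.
- **That the gap biases the comparison or costs meaningful power.** The schedule is the same for both blinded arms, and the person-time involved is very small.

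**Conclusion.** The point holds as a minor error in the current text. Appendix B 5.01 misstates the enrollment period and total duration given II.D and XIII, and the 9.01(c) table stops drug and visits at month 54 when planned follow-up can reach month 61. This rests on the II.D note and Section XIII, not on the summary of changes in the preface.

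The consequence is conditional and small: up to about 6.6 months without scheduled drug for the earliest surviving enrolees, and under 1% of person-time. That share is an upper bound for the assumed uniform accrual and 10% to 15% mortality. It supposes that every site follows the table and that every survivor is still on drug, although Appendix A projects about 16% cumulative permanent discontinuation on bucindolol. Accrual concentrated in the first seven months would raise it. Alpha, power, sample size and the analysis are unaffected.

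Two other differences between Appendix B and the main text are real but trivial and unrelated to the extension. Appendix B gives the higher target dose above 75 kg, where II.C and VII.D.2 give it at 75 kg or more; only a patient at exactly 75 kg is affected. For heavier patients in week 6, Appendix B 6.01(a) has 75 mg BID and VII.D.2 has 100 mg BID, a one-week difference within a flexible titration.

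**What to change.** - **Appendix B 9.01(c):** dispense drug at month 54 and at later visits (for example month 60) until close-out, with de-titration under 9.03 at study end.
- **Appendix B 5.01:** give about 43 months of enrollment and about 5.1 years in total.
- **Separate housekeeping:** set the Appendix B weight cut-points (6.01, 6.01(a), 6.02) to 75 kg or more and less than 75 kg at randomization, and print one week-6 dose for heavier patients (75 or 100 mg BID) in both VII.D.2 and Appendix B 6.01(a).

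The cost is revised Appendix B pages, one line of VII.D.2 if its week-6 dose is the one changed, a pharmacy notice, and some further maintenance bottles for early enrolees still in follow-up. Sample size and analysis do not change, and the main-body visit schedule already covers the later visits.

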It is important to identify which patients will receive the most survival benefit from beta-adrenergic blocking agents. There is a reasonable possibility that the treatment effect of beta-blockers in patients with heart failure may be different in patients with and without coronary artery disease. For the purposes of this study, coronary artery disease will be defined as a history of previous myocardial infarction and/or evidence of significant obstruction (>70% diameter luminal narrowing) of at least 1 major epicardial artery. Two previous ventricular function studies of beta-blocker therapy comparing its effect on patients with ischemic versus non-ischemic etiology demonstrated some differential effects on these two groups of patients.^{30,31} In these studies, the patients with idiopathic dilated cardiomyopathy had a more dramatic improvement in ventricular function and size than patients with ischemic heart disease when treated with beta-adrenergic blocking agent for 3 months. However, both groups of patients received benefit in reduction of ventricular size and improvement in ejection fraction at maximal dosages. In addition, patients with idiopathic dilated

cardiomyopathy have been shown to have a greater degree of beta-receptor downregulation than patients with heart failure due to ischemic heart disease.⁷⁰ On the other hand, patients with heart failure due to ischemic heart disease have a greater degree of functional uncoupling of the beta-receptors to both adenylate cyclase activation and the mechanical response to beta-agonist stimulation.⁷⁰ Thus, there is a reasonable chance that beta-adrenergic blockade will have a differential effect on mortality in patients with and without coronary artery disease. This study will examine whether the presence of coronary artery disease will have an impact on all cause mortality changes due to beta-blockade.

Previous studies have demonstrated that left ventricular ejection fraction, ^{71,72} serum sodium concentration,⁴ New York Heart Association (NYHA) functional class, ⁷¹ and plasma norepinephrine^{4,13} are all independent prognostic indicators of mortality in congestive heart failure. However, it is not known if they modify the effects of beta-blockade in all cause mortality.

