1. Baseline data collection

The baseline visit must be at least 7 days after the screening visit to ensure the clinical baseline stability of the patient. If after review of the inclusion and exclusion criteria, clinical laboratory and MUGA the results do not exclude the patient from participation in the trial, the patient may be randomized. The patient must be NYHA functional class III or IV at the time of the baseline visit in order to be randomized. If at this time, the patient in the opinion of the investigator is clinically unstable, his/her therapy may be changed, and randomization cannot occur until the patient is deemed stable. The patient may be randomized at any time point after all baseline data collection has occurred as long as the Quality of Life questionnaires, clinical laboratory, chest x-ray, and electrocardiogram have been performed within 14 days of randomization. The MUGA must have been performed within 60 days of randomization. Plasma norepinephrine will be collected at the randomization visit before study medication is dispensed.

2. Randomization to drug

Patients will be randomized to coded study drug by the Cooperative Studies Program Coordinating Center in response to a phone call at the baseline visit. The site coordinator will fax the randomization form to the center. An adaptive allocation procedure will be used to randomize patients within a hospital site, balancing treatment groups with respect to presence/absence of coronary artery disease, ejection fraction, race and gender. Every effort should be made by the investigator to determine the etiology of ventricular dysfunction. However, cardiac catheterization is not mandated for entry.

D. Drug Administration

1. Initial drug administration

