The primary objective of this study is to determine whether treatment with beta-adrenergic blockade compared to placebo reduces all cause mortality in patients with moderate to severe congestive heart failure who are concurrently receiving optimal medical therapy. The null hypothesis to be tested is that there is no difference in survival time between active and placebo arms.

Two-tailed treatment comparisons will be made by the nonparametric logrank statistic with the exact variance calculation stratified by site, presence/absence of CAD and gender. This statistic is the optimal nonparametric test when censoring is equal in the treatment groups under proportional hazards. The analysis will include all survival times for all randomized patients in the treatment group to which the patient had originally been assigned (intention-to-treat principle). Significance levels will be set in accordance with the plan for monitoring the study.

Cumulative survival curves will be constructed by Kaplan-Meier methods.⁷⁹ The Cox life table regression method⁸⁰ will also be used to calculate estimates of relative risk, provided the model fits the data.

3. Secondary Objectives

Treatment differences will be evaluated in cause-specific cardiovascular mortality: total cardiovascular mortality, sudden death, worsening congestive heart failure, and ischemic cardiac events. These outcomes will be classified by the Mortality Committee which will remain blinded to treatment assignment. Cause-specific mortality will be further examined to estimate if treatment effect is similar for the different causes of death. Also, the cost of the two therapies will be examined.

The frequency of adverse effects in each treatment group will be analyzed using the chi-square statistic.

4. Subgroup analyses

All prior subgroup hypotheses related to treatment effect modification will be examined with tests to detect significant interactions. Our clinical interest focuses on qualitative interactions. We will use appropriate methods such as Cox regression⁸⁰ and stratified Kaplan-Meier curves.⁷⁹ However, the power to detect differences in treatment effects among subgroups will generally be lower than the power to detect an overall treatment effect. If tests of interaction are significant, then estimates of treatment effect will be derived within each subgroup. All reports of differences based on data-derived subgroups will be identified as such.

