APPENDIX A - SAMPLE SIZE AND RATIONALE

A. Overview

The primary objective of this study is to evaluate the effectiveness of beta-blocker therapy in reducing all cause mortality in patients with moderate to severe congestive heart failure who are receiving concomitant optimal medical therapy. The study is planned as a double-blind, two-arm clinical trial of NYHA class III-IV patients with ejection fraction ≤ 0.35 randomized to either the placebo or beta-blocker (bucindolol) groups. The primary endpoint is time to death. We estimate that 2800 patients will be required to detect with 85% power a 25% annual mortality reduction with bucindolol therapy, taking into account several factors that tend to reduce power. Our approach to sample size was a) to calculate the required number of patients for a range of reasonable design assumptions; b) decide on a sample size; and c) carry out a sensitivity analysis for the fixed sample size in order to evaluate the impact of misspecification of assumptions on the power of the trial.

While there are many approaches to calculating sample size for time-to-event data, the method of Lakatos^{81, 82} was used because it provides estimates of sample size for tests based on the logrank statistic after adjusting for complex trial characteristics such as staggered accrual, time-varying hazard ratios, a lag in treatment effect, losses to followup, noncompliance, and heart transplantation. The adjustment is accomplished by assuming a placebo death rate and percent mortality reduction with treatment (or equivalently a hazard reduction) in a "perfect" trial and then adjusting the rates based on a schedule over time of losses, noncompliance, etc. The observed mortality reduction after adjustment will be lower than before adjustment.

Although randomization will be stratified by hospital site, presence/absence of coronary artery disease, ejection fraction, race and gender, we did not incorporate stratification in the sample size calculations and instead assumed average rates across strata.

B. Assumptions

The target sample size of 2800 patients (1400 per group) was based on the following assumptions (annual rates for mortality, losses to follow-up, noncompliance, and heart transplantation refer to patient years on study, not calendar time):

- 1. Significance level (Type I error) of 5%, two-sided
- 2. **Power** (sensitivity) of 85%

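### The 85% power belongs to an unstratified logrank; the primary test, crossed by about 90 sites, CAD and gender, has about 80%

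*Protocol*

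**What the plan says.** Section VIII.B.2 (Primary Objective) makes the treatment comparison with a two-tailed "nonparametric logrank statistic with the exact variance calculation stratified by site, presence/absence of CAD and gender". Section III.C plans ninety centres. No pooling of small sites or cells is described.

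Appendix A, section A, estimates that "2800 patients will be required to detect with 85% power a 25% annual mortality reduction with bucindolol therapy". Table 1 there gives 2790 patients and 916 deaths, at a "Significance level (Type I error) of 5%, two-sided". The same overview says of the stratified randomisation that "we did not incorporate stratification in the sample size calculations and instead assumed average rates across strata".

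The lists of factors differ:

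- **Section VII.C.2:** allocation takes place within site, "balancing treatment groups with respect to presence/absence of coronary artery disease, ejection fraction, race and gender". Section II.C and Appendix A name the same five factors.
- **Section VIII.B.2:** the test uses three of the five and leaves out ejection fraction and race.
- **Appendix B, section 5.01:** patients are "stratified according to (1) the hospital site and (2) the presence or absence of coronary artery disease", which is two factors.

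Section IV.E says that ejection fraction and three other baseline measures "are all independent prognostic indicators of mortality in congestive heart failure".

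**The concern.** A stratified logrank compares the arms only within a stratum. A death in a cell where one arm has nobody left at risk adds zero to both the score and its variance. A death in a small, uneven risk set adds less than it would in a large balanced one. With about 9 patients and 3 deaths per cell, both happen often enough to matter.

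The test remains valid. What is at stake is information: some of the 916 planned deaths would not count in the primary comparison. The stated 85% would not be the power of the stated analysis, and anyone judging the trial's ability to detect its target effect would be using the wrong figure.

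**Working it through.** **1. Reproduce the plan's figure.** Inputs from Appendix A, section B: 15% against 11.25% annual mortality, 3-year uniform intake, 4.5-year trial, 3-month lag, 1% annual loss, noncompliance 10% then 2% per year, transplantation 1.85% against 0.37% from year 2, 80% of transplanted patients otherwise dying within a year. A Lakatos-type model for an unstratified logrank gives:

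| Quantity | Recomputed | Protocol |
|---|---|---|
| Power at 2800 | 85.3% | 85% |
| N for 85% power | 2775 | 2790 |
| Deaths | 921 | 916 |
| Power, no transplants | 96.0% | 96% |
| Power, 6-month lag | 72.3% | 72% |
| Power, 20% reduction | 60.5% | 60% |
| Power, 10% placebo rate | 55.5% | 57% |
| Power, 25% noncompliance | 79.1% | 81% |

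The 85% therefore reproduces, for an unstratified test. The average hazard ratio it implies is exp(−2 × (1.960 + 1.036)/√916) = exp(−0.198) = 0.82.

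**2. Count the cells.** 90 × 2 × 2 = 360, and 2800/360 = 7.8 patients each. Section V.C targets 50% women at non-VA sites, two thirds of the total. The share at VA sites is not given. Assuming 2% there and 58% CAD, about 304 to 316 cells are occupied: 2800/316 = 8.9 to 2800/304 = 9.2 patients, and 916/316 = 2.9 to 916/304 = 3.0 deaths.

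**3. Why information is lost.** A death contributes p(1 − p), where p is the treated share of its risk set; the maximum is 0.25. One against two gives 2/9 = 0.222 (89% of the maximum), one against three gives 3/16 = 0.188 (75%), and a one-arm risk set gives 0. Under within-site minimisation about 6.5% of deaths fall in one-arm risk sets.

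**4. Size of the loss.** The ratio r is stratified over unstratified logrank variance, from simulation of 2800 patients at hazard ratio 0.82. Then power = Φ(2.996 × √r − 1.960). The last column is direct rejection rates, with a Monte Carlo error of about 1 to 1.6 points.

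| Allocation, site sizes | Cells | r | Power from r | Direct: unstratified → as written |
|---|---|---|---|---|
| Minimisation, equal | 316 | 0.882 | 80.3% | 85.7% → 81.8% |
| Minimisation, uneven | 304 | 0.887 | 80.6% | 84.5% → 81.3% |
| Simple, equal | 316 | 0.822 | 77.5% | 84.5% → 75.5% |
| Simple, uneven | 304 | 0.835 | 78.2% | 84.4% → 77.9% |
| Balanced within each cell | 316 | 0.913 | 81.7% | 83.9% → 81.1% |

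No allocation scheme tried restores 85%. As a cross-check, 916 × 0.885 = 811 effective deaths, close to the 799 that Table 1 gives for 80% power. Recovering 85% would take about 916/0.885 = 1035 deaths, or 2790/0.885 = 3153 patients.

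**5. What drives it (minimisation).**

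- Site alone: r = 0.97, a loss of roughly 0 to 2 points.
- Site × CAD × gender: r = 0.88 to 0.89.
- The same with ejection fraction and race also crossed, each taken as binary: about 900 to 1025 cells, r = 0.59 to 0.64, power about 65 to 69%.
- Ejection fraction, race, CAD and gender without site (16 cells): r = 0.99.

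**6. Variations.** With assumed differences in risk between sites and patient groups, the unstratified test also loses power, and the gap is 3 to 4 points (83.8% to 79.8%; 81.6% to 78.7%). The Preface and Section II.D record a 7-month accrual extension. With 43 months of uniform accrual, 2800 patients and 18 months' minimum follow-up, deaths rise to about 990. The unstratified power is then 87.7%, and at r = 0.88 the test as written has about 83%.

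**The case against.** The strongest reply has four parts.

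- **The omission is disclosed, and a similar loss is accepted.** Appendix A says openly that stratification was left out. Its section C calls a fall from 85% to 81% acceptable when noncompliance is higher than planned. This stands as context, but disclosure does not give the size of the loss, and section C never varies the stratification. The accepted loss was also for a contingency. The stratification loss is built in and comes on top: at 81%, (1.960 + 0.878) × √0.885 − 1.960 = 0.71, or about 76%.
- **The 80% rests on inputs the protocol does not give.** These are full crossing of the three factors, the CAD share, the proportion of women at VA sites, the minimisation probability and the spread of site sizes. It also uses the original 3-year accrual. All of this stands, and is why a range is given.
- **Site is the unit within which patients are allocated, so stratifying on it follows the design.** This stands. Stratifying on site alone costs little; the cost comes from crossing it further.
- **The exact variance deals with sparse cells.** It protects validity. It does not recover information from one-arm risk sets.

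A reader might also infer that leaving ejection fraction and race out of the test causes the loss. The documents do not support that. Adding them to the cross with site would make it much worse. Their absence, and the short list in Appendix B, is a separate inconsistency.

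**Conclusion.** The point holds as a mismatch between the stated power and the stated primary test. The 85% is right for an unstratified logrank. For the test in Section VIII.B.2, within-site minimisation loses about 11 to 12% of the information and leaves power at about 80%, with a range of about 76 to 83%. The low end is simple randomisation; the high end assumes that the extended accrual still yields 2800 patients. The figure assumes fully crossed cells, about 58% CAD and few women at VA sites.

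It would go too far to call the primary test invalid or biased: nothing in the documents points to a type I error problem. Nor is 80% exact. It is a central value under assumptions that the sponsor can replace with actual site and patient counts.

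**What to change.** Do one of two things:

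1. **Keep the test and correct the power.** State in Appendix A that the site × CAD × gender test has about 80% power, give the range and its assumptions, and recompute with the extended accrual and actual site sizes.
2. **Use coarser strata.** Stratify the primary logrank by site alone (about 97% of the information), or by CAD × gender × VA versus non-VA. The latter is 8 cells; it was not simulated itself, but 16 cells without site kept 99%. Show the fully crossed test as a sensitivity analysis.

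The second option should be settled while the Steering Committee has no access to endpoint data (Section III.A). The Preface requires approval by that committee, the DSMB, the VA and NHLBI. The DSMB already sees treatment comparisons, so the record should show that the proposal came from the blinded side. The statistical cost is small: differences in risk across site-by-CAD-by-gender cells are no longer fully conditioned on.

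Separately, reconcile the factor lists in Sections II.C and VII.C.2 and Appendix A with the list in Appendix B, section 5.01. If ejection fraction and race are to enter the analysis, use them as covariates or as strata without site, with their categories stated, and not as further factors crossed with site.
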